1.2.3 Clinical Study Data for Loncastuximab Tesirine and Idelalisib

Loncastuximab tesirine

ADCT-402-101 (NCT02669017, <https://clinicaltrials.gov/ct2/show/NCT02669017>), was a first-in-human Phase 1 dose-escalation study of loncastuximab tesirine in R/R B-cell NHL patients. The data from this study showed loncastuximab tesirine exhibits significant anti-tumor activity in heavily pretreated patients with R/R FL, with an ORR of 78.6% and a CRR of 64.3%. Median duration of response and median progression free survival (PFS) were both not reached.

Toxicity was manageable, with the most common Grade ≥ 3 treatment-emergent adverse events (TEAEs) being Gamma-glutamyl transferase (GGT) increased (21.3%); neutropenia (16.9%); anemia (15.3%); neutrophil count decreased (14.8%); thrombocytopenia (12.0%); platelet count decreased (10.4%); blood alkaline phosphatase (ALP) increased (6.6%); lymphocyte count decreased (6.6%); disease progression (6.0%); febrile neutropenia (5.5%); and hypokalemia (5.5%) ([Loncastuximab tesirine IB](#))

Idelalisib

Idelalisib is the only PI3K inhibitor approved by FDA and EMA as monotherapy for the treatment of adult patients with FL that is R/R to two prior lines of treatment.

In Study 101-09 (NCT01282424, <https://clinicaltrials.gov/ct2/show/NCT01282424>), 72 patients with FL received 150 mg of idelalisib orally twice (BID) daily until evidence of disease progression or unacceptable toxicity. The ORR was 55.6% and CRR was 16.7%. The median PFS was 11.0 months (range 8.0–14.0), and the median DOR was 11.8 months (range 6.2–26.9) ([Idelalisib -SmPC](#)).

The most common Grade ≥ 3 TEAEs in 125 adults with indolent non-Hodgkin lymphoma treated with idelalisib 150 mg BID in clinical trials were elevated transaminases (21%), diarrhea (13%), neutropenia (27%), pneumonia (7%), and thrombocytopenia (6%) (Gopal et al, 2014).

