5.5.1 Discontinuation from Study Treatment

A patient may be discontinued from the study treatment for any of the following reasons:

- Disease Progression
- Adverse events
- Patient decision

- Physician decision
- Major protocol deviation
- Lost to follow-up
- Study termination by the Sponsor

A patient must discontinue from the study drug for any of the following reasons:

- Pregnancy
- Death

The reason(s) patients initiate subsequent anti-lymphoma therapy should be captured.

IMPORTANT: Study treatment discontinuation is not equivalent to discontinuation from the study. Patients discontinuing the study treatment will be asked to perform an EOT visit ([Section 4.2.4](#)) and continue with the Follow-up period ([Section 4.2.5](#)) as per protocol.

The investigational site should make every effort to complete follow-up per protocol. If patients are unable to return to the site, patient status, including but not limited to survival status, may be obtained by site staff via phone, email, or mail.

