Grade 4 infusion related reaction	
• Permanently discontinue loncastuximab tesirine
Hy's law (AST and/or ALT $> 3 \times \text{ULN}$ and bilirubin $> 2 \times \text{ULN}$)	
• Permanently discontinue loncastuximab tesirine. Hy's law defined as: AST and/or ALT $> 3 \times \text{ULN}$ and bilirubin $> 2 \times \text{ULN}$, and without initial findings of cholestasis (ALP activity $< 2 \times \text{ULN}$) and no other reason that could explain the combination of increased transaminases and serum total bilirubin, such as viral hepatitis A, B, or C, preexisting or acute liver disease, or another drug capable of causing the observed injury

Table 5. Criteria for Dose Delay or Dose Modification of Idelalisib

Toxicity	Idelalisib
Grade ≥ 2 symptomatic pneumonitis of any severity	Permanently discontinue idelalisib
Grade 2 increased ALT/AST/bilirubin or diarrhea	Maintain idelalisib dose. Monitor at least weekly until normal
Grade 3 increased ALT/AST/bilirubin or diarrhea	Withhold idelalisib. Monitor at least weekly until normal, then may resume idelalisib at 100 mg BID.
Grade 4 increased ALT/AST/bilirubin or diarrhea	Discontinue idelalisib permanently
Grade 3 neutropenia and/or thrombocytopenia	Maintain Idelalisib dose. Monitor ANC and/or platelet count at least weekly
Grade 4 neutropenia and/or thrombocytopenia	Withhold idelalisib. Monitor ANC and/or platelet count at least weekly. When neutropenia and thrombocytopenia are Grade 3 or less, may resume idelalisib at 100 mg BID
Grade ≥ 3 sepsis or pneumonia	Withhold idelalisib until infection has resolved.
Active CMV infection of any grade or viremia (positive PCR or antigen test)	Withhold idelalisib until the infection and viremia have resolved. If idelalisib is resumed, monitor by PCR or antigen for CMV reactivation at least monthly.
Suspected PJP infection of any grade.	Withhold idelalisib. Permanently discontinue idelalisib if PJP infection is confirmed.
Other Grade ≥ 3 non-hematologic toxicities	Withhold idelalisib until resolved, then may resume idelalisib at 100 mg BID. If the same grade ≥ 3 toxicity recurs after resuming idelalisib, permanently discontinue idelalisib
Anaphylaxis, Intestinal Perforation, Stevens-Johnson syndrome (SJS) and toxic epidermal necrolysis (TEN)	Permanently discontinue idelalisib

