Abbreviations: ALT=alanine aminotransferase; ANC= Absolute neutrophil count; AST=aspartate aminotransferase; BID=twice daily; CMV=cytomegalovirus; PCR=polymerase chain reaction; PJP=Pneumocystis jirovecii pneumonia.

Reference: [Idelalisib® Prescribing Information](#) For additional information on management of toxicities, please refer to the [Investigator Brochure for loncastuximab tesirine](#) and to the [prescribing information](#) or [SmPC](#) for idelalisib.

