7.4.5 Laboratory Tests

Samples will be collected at the time points specified as per SoE ([Table 1](#) or [Table 2](#)).

Additional sample(s) may be collected and analyzed if clinically indicated. The C1D1 laboratory tests do not need to be repeated if the laboratory tests for eligibility were done within 3 days of C1D1.

Hematology: red blood cell (RBC), white blood cells (WBC) with 5-part differential (neutrophils, eosinophils, basophils, lymphocytes, and monocytes), platelet count, hemoglobin, and hematocrit.

Chemistry: ALT, AST, GGT, ALP, amylase, lipase, total bilirubin (conjugated and unconjugated bilirubin only when total bilirubin is abnormal), sodium, potassium, chloride, phosphorus/phosphate, calcium, magnesium, blood urea nitrogen or urea, carbon dioxide/bicarbonate, creatinine, creatinine clearance, creatine phosphokinase, total protein, albumin, glucose, and lactate dehydrogenase, uric acid.

Coagulation: partial thromboplastin time (PTT)/activated PTT (aPTT) and International Normalized Ratio (INR).

Urinalysis: pH, specific gravity, protein, WBC, RBC, ketones, glucose, and bilirubin.

Urinalysis may be performed by dipstick. Abnormal findings will be followed up with a microscopic evaluation and/or additional assessments as clinically indicated. A microscopic evaluation consists at a minimum of WBC and RBC quantitation per high power field, as well as semi-quantitative assessment of other cells and substances, if present, such as epithelial cells, bacteria, and crystals (“few,” “moderate,” “many”). Other evaluations depending on microscopic findings may be added.

Other tests:

HBV and/or HCV serology tests, and viral load test if clinically indicated.

HIV serology tests, and HIV viral load and /or CD4+ T cell count if clinically indicated.

CMV screening tests: CMV IgG test, and CMV antigen or PCR test for all patients during screening period.

CMV monitoring tests: CMV antigen or PCR test for patients with positive CMV serology or history of CMV infection who are receiving treatment with idelalisib.

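### Table 5 has no combined transaminase-bilirubin rule, so an idelalisib patient who meets Table 4's Hy's-law definition without a Grade 4 value has no mandatory permanent stop

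*Combined protocol and SAP*

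**What the plan says.** Section 6.7.1 gives each drug its own dose-modification table.

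- **Table 4 (loncastuximab tesirine)** has a Hy's-law row: "Permanently discontinue loncastuximab tesirine. Hy's law defined as" AST and/or ALT above 3×ULN with bilirubin above 2×ULN, ALP below 2×ULN, and no other explanation such as viral hepatitis, liver disease or another drug.
- **Table 5 (idelalisib)** has three liver rows, each keyed to the grade of ALT, AST or bilirubin. Grade 2: "Maintain idelalisib dose. Monitor at least weekly until normal". Grade 3: "Withhold idelalisib. Monitor at least weekly until normal, then may resume idelalisib at 100 mg BID". Grade 4: permanent discontinuation. No row looks at transaminases and bilirubin together.
- **Recurrence.** Table 5's only stop-on-recurrence rule, "toxicity recurs after resuming idelalisib, permanently discontinue idelalisib", sits in the row for other non-hematologic toxicities of Grade 3 or higher.
- **Other routes to stopping.** Section 4.2.3 lets treatment run until progression, unacceptable toxicity, death or another discontinuation criterion. Section 5.5.1 lists adverse events and physician decision under "A patient may be discontinued from the study treatment for any of the following reasons". Its separate list of reasons that compel discontinuation contains only pregnancy and death.
- **Outside sources.** The note under Table 5 cites the idelalisib prescribing information and adds: "For additional information on management of toxicities, please refer to the" brochure for loncastuximab tesirine and the label or SmPC for idelalisib. Section 6.3 also refers to the label or SmPC for idelalisib instructions.

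**The concern.** Combined transaminase and bilirubin elevation with no cholestasis and no other cause is a pattern that the sponsor itself judged serious enough to end treatment, since it wrote that rule into Table 4. Idelalisib is the arm for which the protocol names ALT and AST elevations among the most common laboratory abnormalities (Section 1.3), yet that arm's table has no matching rule. An investigator who follows Table 5 literally could keep a patient on drug, or restart one, after injury that would be a permanent stop in the other arm. What is at stake is patient safety and consistent handling across sites. The efficacy inference is not in question.

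**Working it through.** The plan states no figure on this point, so the main check is a reading of the two tables side by side.

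**Step 1. Apply both tables to one patient.** Take a patient who meets every element of the Table 4 definition: AST and/or ALT >3×ULN, bilirubin >2×ULN, ALP <2×ULN, no other explanation. Where two Table 5 rows apply, assume that the higher grade governs.

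| Highest grade among ALT, AST, bilirubin | On loncastuximab tesirine (Table 4) | On idelalisib (Table 5) |
|---|---|---|
| No value above Grade 2 | Permanent stop | No hold; the Grade 2 row keeps the dose, with at least weekly monitoring |
| At least one Grade 3, none Grade 4 | Permanent stop | Mandatory hold; restart at 100 mg BID allowed once normal |
| Any Grade 4 | Permanent stop | Permanent stop |

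The arms agree only in the last line. Section 8.3 grades events by CTCAE v5.0, but the documents do not print its laboratory cut-offs, so they do not show how such patients would divide between the first two lines. The conclusion does not need that split: neither line contains a mandatory permanent stop.

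**Step 2. Look for another rule that closes the gap.**

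- *Recurrence rule.* It belongs to the row for other toxicities. ALT, AST and bilirubin have rows of their own, so by its wording it does not reach them. A second Grade 3 liver value triggers another hold, and the table states no limit on restarts.
- *Section 5.5.1.* Adverse events and physician decision permit stopping; they do not require it.
- *Section 4.2.3.* Unacceptable toxicity ends treatment, but the term is not defined and needs a judgment in each case.
- *Section 4.3.* No stopping rule is specific to the liver, and all three only pause enrollment.
- *Label and brochure.* Their content is not in the documents.

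Nothing in the protocol's own text makes permanent discontinuation mandatory for this pattern.

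**Step 3. How often might the liver rows be used?** Inputs: Section 1.2.3 gives Grade 3 or higher elevated transaminases in 21% of 125 idelalisib patients with indolent lymphoma; Section 9.1 gives about 150 patients at 2:1, so 150 × 1/3 = 50 on idelalisib.

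- Count behind 21%: 26/125 = 20.8%. Neighboring counts give 25/125 = 20.0% and 27/125 = 21.6%, so 26 is the only one that rounds to 21%.
- Exact (Clopper-Pearson) 95% interval for 26/125: 14.06% to 28.97%.
- Expected number among 50: 50 × 0.208 = 10.4. Interval for the expectation: 50 × 0.1406 = 7.0 to 50 × 0.2897 = 14.5.

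The 7.0 to 14.5 carries only the uncertainty in the historical rate. Sampling variation among 50 patients at 20.8% would by itself give roughly 5 to 16.

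This is a count of patients likely to reach the Grade 3 or Grade 4 liver row on transaminases alone. It says nothing about concurrent bilirubin, ALP or alternative causes, it includes Grade 4 cases that Table 5 already stops, and it leaves out patients whose transaminases stay below Grade 3. It cannot be converted to a Hy's-law rate.

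**The case against.** The strongest reply is that idelalisib is an approved drug managed by its label. Tables 4 and 5 are offered as summaries, Table 5 cites the prescribing information, Section 6.3 defers to the label or SmPC, and Amendment 3 aligned idelalisib laboratory monitoring with the SmPC. Different drugs may properly have different rules, and Table 5 is in some respects the stricter table: a Grade 3 liver value must return to normal and any restart is at a reduced dose, whereas Table 4's general non-hematologic row asks only for Grade 1 or lower and reduces the dose only after a delay of more than three weeks. Restart is permitted, not instructed, and a hepatic injury with no other explanation could well be judged unacceptable toxicity.

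Much of this stands. The gap is established for the protocol text only; the label may or may not close it. It does not remove the point. The protocol offers those sources as additional information, and Table 5 itself writes out permanent stops for other serious events, among them pneumonitis, confirmed PJP and intestinal perforation. For this pattern its own rows point toward keeping or restarting the drug, and the remaining safeguards are discretionary.

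Three stronger readings are tempting and are not supported:

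- A reader might infer that the protocol requires continued dosing through Hy's law. It does not: Grade 3 forces a hold, Grade 4 a permanent stop, and the investigator may stop at any time. Whether such a patient could stay at Grade 2 depends on cut-offs that the documents do not print.
- A reader might take the roughly 10 patients above as Hy's-law cases. They are not, for the reasons given with the calculation.
- A reader might see a mirror-image defect in Table 4, which has no row for SJS/TEN while Table 5 has one. The documents report no SJS/TEN on loncastuximab tesirine, and the entry exclusion for a history of it may be there because of idelalisib. That difference may simply reflect drug-specific risk.

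**Conclusion.** The point holds for the protocol's written rules. An idelalisib patient who meets the full Table 4 Hy's-law definition with no Grade 4 value has no mandatory permanent discontinuation, and the liver rows carry no stop on recurrence. Stopping depends on investigator judgment or on a label that cannot be checked here.

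The number of patients affected cannot be estimated from the documents. The 21% transaminase figure supports only the statement that the liver rows will be used in an arm of about 50. The conclusion assumes that the recurrence rule is read as worded and that the cited label does not act as an overriding mandatory rule. This is a patient-safety gap worth closing in the next amendment; power, alpha and the CRR analysis method are unaffected.

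**What to change.** Add a Hy's-law row to Table 5 that uses the complete Table 4 definition, requires permanent discontinuation of idelalisib, and is stated to override the Grade 2 and Grade 3 liver rows. Keep the ALP and no-other-cause conditions: inclusion criterion 8d admits patients with Gilbert's syndrome with bilirubin up to 3×ULN, and a bare bilirubin threshold could stop some of them wrongly.

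State that an ALP is to be obtained when a Day 15 draw flags a possible case. The Day 1 panel already covers it ("Chemistry: ALT, AST, GGT, ALP, amylase, lipase, total bilirubin"), but the Day 15 draws in Cycles 1 to 4 (Table 2) measure only AST, ALT and total bilirubin. Section 7.4.5 already allows additional samples when clinically indicated, so this adds one test in flagged patients and no new visit type.

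The cost is one table row and no extra patients. The downside is a few more mandatory stops, including some patients who might have tolerated rechallenge, and a protocol rule placed on top of the cited label.

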6.8 Supportive Care

Supportive care specific to loncastuximab tesirine are detailed in below subsections. Additional information is available in the [loncastuximab tesirine IB](#). Supportive care for idelalisib should be provided based on the idelalisib prescribing information or SmPC, and/or according to institutional SOC.

6.8.1 Management of Edema and Serosal Effusion

Spironolactone at standard doses should be administered for patients with weight gain greater than 1 kg from Cycle 1 Day 1, new or worsening edema, and/or new or worsening serosal (pleural, pericardial, or ascitic) effusion. The dose of spironolactone may be titrated as clinically indicated. Additional diuretic support may be added if there is further increase in weight, edema, or effusion. Additionally, patients should be advised to monitor their weight daily, at around the same time (preferably in the morning), and to notify the study site if they gain >1 kg (2.2 pounds) over baseline.

6.8.2 Prevention and Management of Infusion-related Hypersensitivity Reactions

Medications for the treatment of severe hypersensitivity reactions, including anaphylaxis, should be available for immediate use and may be administered according to site standard treatment protocols.

Any patient who experiences an infusion-related hypersensitivity reaction should receive prophylactic treatment in subsequent cycles according to the guidelines below or institutional SOC:

- On Day 1 of each cycle, patients will be instructed to take dexamethasone 20 mg PO or equivalent 12 and 6 hours before the start of the loncastuximab tesirine infusion. When necessary, 12 and 6 hours before the first infusion may be defined as “immediately before sleeping” and “immediately after waking up.”
- On Day 1 of each cycle, patients will be given diphenhydramine hydrochloride 50 mg IV 30 minutes before the start of the loncastuximab tesirine infusion.
- On Day 1 of each cycle, patients will be given ranitidine (or equivalent) 50 mg IV 30 minutes before the start of the loncastuximab tesirine infusion.
- For 2 days following administration of loncastuximab tesirine on Day 1, patients are to take dexamethasone 4 mg PO BID.

6.8.3 Prevention and Management of Skin Toxicity

Skin toxicity has been reported in patients receiving loncastuximab tesirine for hematologic malignancies. Often, the toxicities manifested as rash were reported in sun exposed areas; it is therefore recommended that precautions are taken to avoid exposure of skin to sunlight, even through glass (e.g., use of sun protective clothing and sunglasses, sunscreen with a sun

protection factor ≥ 30 applied every 2 hours. Also, fragrance-free detergents and soaps are recommended.

Treatment recommendations for skin toxicities include topical treatment to affected areas:

- Maculopapular rash or photosensitivity rash: high potency topical steroid cream (e.g., clobetasol propionate 0.05%, halobetasol propionate 0.05%)
- Pruritus: high potency topical steroid cream (e.g., clobetasol propionate 0.05%, halobetasol propionate 0.05%) and consider oral antipruritic.
- Xerosis or hyperpigmentation: consider ammonium lactate 12% or urea 20% BID; and triamcinolone 0.1% and triamcinolone 0.1% cream BID.
- Blistering rash: silvadene 1% cream BID and consider laboratory testing for blistering disorder (Varicella Zoster Virus (VZV)/Herpes Simplex Virus (HSV) and bacterial infection; bullous pemphigoid; pemphigus)

Consideration should be given to corticosteroid therapy in patients who develop clinically significant skin toxicity. Also, for grade ≥ 2 skin toxicities consider a dermatology consult.

6.8.4 Contraceptive Guidance

Women of childbearing potential* must agree to use a highly effective method of contraception, and men with female partners who are of childbearing potential must agree to use a condom when sexually active or practice total abstinence from the time of giving informed consent until the study drug is safely cleared from the body. Please refer to [Section 5.1](#) Inclusion Criterion #9 for information on the definition of WOCBP and recommended highly effective methods of contraception.

- For patients with loncastuximab tesirine treatment, if applicable, the highly effective birth control must be followed from the date of signing the ICF until at least 9 months after last dose of loncastuximab tesirine administration for WOCBP, and at least 6 months after the last dose of loncastuximab tesirine for male patients with female partners of reproductive potential.
- For patients with idelalisib treatment, if applicable, the highly effective birth control must be followed from the date of signing the ICF until 1 month after the last dose of idelalisib for WOCBP, and 3 months after the last dose of idelalisib for male patients with female partners of reproductive potential.
- If WOCBP use hormonal contraceptives such as birth control pills, a second barrier method of contraception (e.g., condoms) must be used during idelalisib treatment until 1 month after last dose of idelalisib.

Please refer to [Section 7.4.6](#) for pregnancy test, and [Section 8.5.2](#) for reporting pregnancy.

6.8.5 Other Supportive Care

- Patients receiving idelalisib treatment should receive *Pneumocystis jirovecii* pneumonia (PJP) prophylaxis based on institutional standard of care.
- Patients receiving idelalisib and who have positive CMV serology or a history of CMV infection should be monitored for CMV viremia using CMV antigen or PCR. Patients who develop CMV viremia should have idelalisib held and CMV treatment based on institutional standard of care.
- Although the study patient population has a low risk for development of tumor lysis syndrome (TLS) compared to patients with acute disease ([Cairo et al, 2010](#)), patients should be observed for development of TLS and treated according to site standard treatment protocols.
- As testing in animals showed testicular toxicity (atrophy with reduced spermatogenesis), male patients are advised to consider cryopreservation of sperm prior to treatment with loncastuximab tesirine, where applicable.

6.9 Concomitant Medications and Procedures

Medications (except for the study treatment) and procedures will be recorded in the eCRF starting from the ICF signature date or from 14 days prior to C1D1, whichever is earlier, and continuing until at least 30 days after last dose of study treatment.

6.9.1 Permitted During Study

Medications or procedures for the clinical care of the patient, including management of AEs, are permitted during the study, except for those listed in [Section 6.9.2](#).

6.9.2 Prohibited During Study

The following treatments are prohibited during study treatment but are allowed in the follow-up period.

- Other anticancer therapy with the exception of hormonal therapy for maintenance treatment of breast and prostate cancer.
- Other investigational agents
- Live vaccines until 3 months after last dose of study drug.
- In patient receiving idelalisib, strong CYP3A inducers/inhibitors and sensitive substrates should be avoided. Information on strong CYP3A inducers, inhibitors and sensitive substrates may be found in [Section 12.3 \(Appendix 3\)](#) or at <http://medicine.iupui.edu/clinpharm/ddis/main-table/>

7 Study Assessments and Procedures

Study assessments and procedures are to be completed as described below; however, there may be situations (e.g., safety issues) preventing their completion. In such case, the Investigator should take all actions necessary to ensure the safety and well-being of the patient and document the reason for not performing the assessment.

The Schedule of Events (SoE) tables are listed per treatment arm for the study. [Table 1](#) is for loncastuximab tesirine arm and [Table 2](#) is for idelalisib arm.

